2. EXTERNAL COLLABORATORS

Not applicable

3. ABSTRACT

Type 1 diabetes mellitus (T1DM) is a challenging medical disorder, especially in children and adolescents. In order to prevent the chronic complications of hyperglycemia, the maintenance of near-normal glycemic control must be balanced with minimizing hypoglycemia [1]. Prior to the 21st century, most individuals were treated with consistent carbohydrate intake and relatively set, or fixed doses of insulin [2]. Over nearly the past twenty years, with the availability of multiple rapid-acting and basal insulin analog preparations, individuals with diabetes have had the ability to utilize a variable carbohydrate and insulin regimen. These diabetics have the ability to eat as much or as little amount of food he/she desires, assuming he/she delivers an appropriate amount of rapid-acting insulin to cover the amount of carbohydrates. The insulin-to-carbohydrate ratio (ICR) is determined through trial-and-error as well as experience [3]. In addition to the use of the ICR, the management of diabetes for most children and adolescents requires consistent parental involvement and supervision [4]. Although children and adolescents with T1DM have much more freedom with the amount of food (carbohydrates) they eat while using an ICR at mealtime, the difficulty in determining the amount of insulin needed, how and when to adjust the ICR, the difficulty with understanding the basics of managing T1DM, and the adaptation to a new lifestyle with T1DM may be more complicated than utilizing a simple plan that includes a fixed amount of insulin and fixed number of carbohydrates, at least for the first few months after diagnosis. As complicated as it is for children, adolescents, and their caregivers to learn how to manage T1DM after being discharged home in usually < 48 hours after diagnosis, a more simplified insulin regimen at mealtime may provide the family of and the child or adolescent with newly diagnosed T1DM with less stress and anxiety while still maintaining adequate glycemic control.

Although many pediatric endocrinologists provide an ICR plan for their newly diagnosed patients with T1DM, fixed dosing and other forms of insulin delivery are available. The objective of this investigator-initiated, prospective proposal is to determine if children and adolescents with T1DM have improved glycemic control and, their families experience less anxiety with a fixed insulin and carbohydrate regimen compared to those using an ICR and variable carbohydrate intake.

4. BACKGROUND

Type 1 diabetes mellitus (T1DM) is an autoimmune disorder characterized by a severe deficiency or absence of endogenous insulin, resulting in chronic hyperglycemia. The achievement of optimal glucose control is facilitated by intensive insulin treatment [5]. The current recommendations are based on the basal bolus

paradigm, with subcutaneous long-acting insulin or continuous subcutaneous infusion of rapid-acting insulin to cover basal requirements and with rapid-acting insulin to prevent or correct glucose excursions. Home blood glucose monitoring has been the mainstay for glucose monitoring for more than 30 years. It provides information about an individual's glucose level and allows individuals to make adjustments as needed to help them manage their glycemic control [6].

Despite advances in medical treatment and technology, nutritional therapy continues to be the cornerstone of diabetes management [7]. Carbohydrates are a major determinant of postprandial blood glucose. Carbohydrate counting is a meal planning approach that focuses on carbohydrates as the primary nutrient affecting postprandial glycemic response. Advanced carbohydrate counting allows adjustment of the prandial insulin dose for actual carbohydrate intake for diabetics using intensive insulin therapy. According to the Bell and Shimin meta-analysis, carbohydrate counting significantly reduced HbA1c concentration in adults [8,9]. Tascini et al reported that carbohydrate counting had a positive effect in children and adolescents with T1DM, by reducing hypoglycemic events and improving quality of life [5]. These studies, however, did not compare different types and amount of insulin for variable carbohydrate intake.

Fixed mealtime carbohydrate with a fixed mealtime insulin dose is a simplified regimen that provides a set amount of insulin for a set amount of carbohydrates and ensures that each dose and each meal is consistent. A set amount of carbohydrate is assigned in grams or portions and patients choose different carbohydrate servings to equal the target amount. This method is easy to use and may be appropriate for patients who are new to taking insulin in that it may improve compliance, glycemic control, and anxiety.

Shortly after diagnosis of T1DM, many children and adolescents not uncommonly experience a honeymoon period [10]. It occurs because there is a sufficient amount of residual B-cell mass that enables some of these individuals to secrete some endogenous insulin. As a result, in order to prevent hypoglycemia, these individuals may be managed with less exogenous insulin over a short period of time [11]. This variability makes less accurate HbA1C concentration as a gold standard for assessing glucose control in the first 6-12 months after diagnosis [12,13].

Glycemic variability (GV) obtained from multiple blood glucose levels (up to 6 – 10 times/day) provides a good correlation for an individual's glycemic control and predictor of chronic diabetic complications [3]. The GV refers to swings in blood glucose levels and captures blood glucose oscillations that occur throughout the day, including hypoglycemic periods, postprandial increases, as well as blood glucose fluctuations that occur at the same time on different days [14]. The proposed target range of 70–180 mg/ dl is considered acceptable for clinical practice, as it has been observed that if 50% of the self-monitoring of blood glucose readings are in this range, the A1C would be ~7% [12,13]. Shapiro et al, reported that teens and parents show some similarities in the facets comprising distress, including negative emotions about diabetes and the demanding diabetes regimen [15]. Simplified insulin treatments will remarkably help to maintain adherence and to prevent deterioration in glycemic control.

For the purposes of this study the following definitions will be used:

BMI: Weight (kg)/ Height (m²).

Glycemic variability: Blood glucose oscillations that occur throughout the day. The glycemic range on target is between 80 – 180 mg/dl.

Insulin dose adjustment: Titration of insulin over time to improve glycemic control.

Parental stress: Stress associated to caring for a child with diabetes.

Insulin to carbohydrate ratio (ICR): Number of carbohydrates that 1 unit of rapid-acting insulin covers.

Basal insulin: Insulin that controls blood sugar consistently for 24 hours.

Rapid-acting insulin: Mealtime insulin. Typically has onset in 10 - 15 minutes, peaks at 45 – 60

5. APPROACH –RESEARCH METHODS

A. STUDY DESIGN

Two - Arm, Randomized, Clinical trial (See Figure 1)

This proposal is designed to compare children and adolescents with newly diagnosed T1DM using a fixed insulin dose for fixed carbohydrate mealtime regimen (FIXED group) to children and adolescents with newly diagnosed T1DM using an ICR with variable carbohydrate intake (ICR group) mealtime regimen and determine:

1) Specific Aim 1

Determine the feasibility for a subsequent clinical trial involving rapid acting insulin dosing for a fixed dose for fixed carbohydrates (FIXED group) vs ICR with variable carbohydrate intake (ICR group) in order to determine the capacity for recruitment, caregiver consent to random assignment and completion of study measures, average session attendance, caregiver treatment adherence, and post-treatment satisfaction.

2) Specific Aims 2

- a) Determine if the caregivers of diabetics using a fixed insulin for fixed carbohydrate regimen (FIXED group) experience less anxiety than the caregivers of those using an ICR with variable carbohydrate intake regimen (ICR group) at 1- and 4-months post-randomization.
- b) Determine if diabetics utilizing a fixed insulin for fixed carbohydrate regimen (FIXED group) have decreased glycemic variability (GV) than those using an ICR with variable carbohydrate intake regimen (ICR group) at 1- and 4-months post-randomization.

We hypothesize that we will recruit and consent enough patients in order to perform a future, larger trial where caregivers of children and adolescents with newly diagnosed T1DM using a fixed insulin for fixed carbohydrate mealtime regimen (FIXED group) will experience less anxiety and their diabetic children will experience less GV than children and adolescents with newly diagnosed T1DM who use an ICR with variable carbohydrate intake at mealtime (ICR group). If this proves to be true, less anxiety may encourage more compliance and better glycemic control.

[figure not shown]

Figure 1: Study design and hypothesis.

3) Methods

a) Recruitment & Consent

Subjects with newly diagnosed T1DM will be evaluated by authorized study personnel under a HIPAA waiver to determine potential eligibility. The subjects will be contacted by the research study team while in the hospital during his or her initial diagnosis to explore his/her interest in the study and to confirm eligibility. The informed consent/assent documents will be signed at the time of the initial contact.

b) Initial Visit (at CHOA-Egleston)

Recruitment of the 20 to 40 pediatric subjects will take place at the Children's Healthcare of Atlanta at Egleston, when they are hospitalized with the diagnosis of new onset T1DM.

Enrolled participants will be interviewed in order to collect demographic information. The subjects will be randomized to either the FIXED group or the ICR group according to a computer-generated random sampling table. The subject and his/her caregivers will receive diabetes education while in the hospital in standard fashion. The subject and his/her caregivers will receive glucose monitoring education and training prior to hospital discharge. The subject and his/her caregivers will also receive a paper log to record the blood sugars, number of carbohydrates consumed, and insulin administered at each meal throughout the day.

Prior to discharge, all subjects will receive a regimen that includes a: 1) Meal-time insulin and carbohydrate regimen (# of units of insulin, # of carbohydrates, and/or ICR);

2) Evening dose of Glargine; 3) Hyperglycemia correction regimen for blood glucose levels > 199 mg/dL; and 4) Hypoglycemia treatment regimen for blood glucose levels < 70 mg/dL and/or symptomatic.

c) After Hospital Discharge and Between Clinic Visits

As per standard diabetes care, caregivers will report all blood glucose levels every day (to the study investigators) until the subject's initial clinic visit 4-6 weeks after diagnosis. All insulin adjustments will be made by the study investigators.

After the subject's first clinic visit, caregivers will contact the study investigators once a week to report blood glucose levels and the investigators will make adjustments as needed.

d) Diabetes Clinic Visits

All the diabetes clinic visits will occur at the Center for Advanced Pediatrics (CAP), approximately three miles from CHOA-Egleston Hospital. Subjects will attend clinic with one or more of the investigators approximately 1 and 4 months after enrollment.

At each clinic visit, subjects and their caregivers will answer standard diabetes questions, undergo a physical examination, and objective data (vital signs, glucose meter (GM) data, insulin dosing, and carbohydrate intake) will be collected by the study personnel.

B. STUDY POPULATION

The plan is to enroll from 20 to 40 children and adolescent subjects with newly-diagnosed T1DM. Twenty will be randomized to the FIXED group and twenty will be randomized to the ICR group. The subjects will be selected from children and adolescents admitted to CHOA-Egleston with a diagnosis of new-onset Diabetes Mellitus. Participation in this study will be determined by a set of inclusion/exclusion criteria.

1) Inclusion Criteria

For enrollment in the study, subjects must: (1) Have Confirmed diagnosis of T1DM based on the most recent ADA criteria [16]; (2) Be 8 - 14 years of age; (3) Begin monitoring with a glucose monitor prior to discharge from the hospital; and (4) Have the ability to understand and be willing to adhere to the study protocol. (5) English or Spanish speakers.

2) Exclusion criteria

For enrollment in the study, subjects may not: (1) Have a clinically significant major organ system disease (i.e., hypertension, hyperlipidemia, or obesity); (2) Be on glucocorticoid therapy; (3) Have Type 2 Diabetes Mellitus; (4) Have Polycystic Ovarian Syndrome (PCOS); (5) Have a BMI > 85th %ile; (6) Have Acanthosis Nigricans; (7) Have any form of renal impairment; (8) Have Cystic Fibrosis; (9) Have Glucocorticoid-, Chemotherapeutic-, or any other Medication-induced form of Diabetes; (10) Be using any basal insulin other than Glargine insulin; (11) Have cognitive impairment (> 2 grades behind age-appropriate grade in school); (12) Be in Foster Care; (13) Have any history of DFCS involvement; and (14) If female, be pregnant or breast-feeding.

C. DATA MANAGEMENT

All data, including patient demographics, history, and laboratory tests will be collected on standardized forms and entered into an electronic database, REDCap. REDCap is a HIPPA-compliant, web-based, data capturing tool used in over 130 countries. Features include user-specific credentials, data-logging, longitudinal data modeling and more. Enrolled patients will be assigned a study ID. Subjects will only be identified in REDCap by their study ID. The patient's name, MRN and study ID will be kept in a secure file in a double lock in a filing cabinet under [name] supervision in the Emory Children's Center. Records will be maintained for 10 years as required for IRB studies.

D. OUTCOME MEASURES

1) Primary Outcome Measures

The primary goal of this study is to determine the feasibility of a subsequent clinical trial of rapid acting insulin dosing for fixed carbohydrates (FIXED group) vs ICR with variable carbohydrate intake (ICR group). In doing so, we will examine our ability to recruit and consent patients (>70% consent rate), study retention (>90% retention), completion of study visits (average session attendance \geq 90%), study measures (\geq 90% measure completion), caregiver treatment adherence, and post-treatment satisfaction (\geq 90%),

2) Secondary Outcomes Measures

Secondary outcome measures will include caregiver anxiety and glycemic variability. Each of these measures are described below.

One secondary outcome measure is caregiver anxiety. This will be assessed by a parental stress scale [17]. The caregiver will fill out the questionnaire at initial enrollment (prior to hospital discharge) and at each clinic follow-up throughout the study. We will use the Spanish adaptation of parental stress scale (PSS) [18] for Spanish population if necessary.

We clarify in the survey that the questions are to be answered in terms of how the caregiver-child relationship exists since the diagnosis of diabetes mellitus.

The scales are shown in **Annex 1 and 2**

Glycemic variability (GV) is another secondary outcome measure. The GV will be calculated in all subjects through the use of a glucose monitor (GM) data classification scale. Subjects will be considered to have appropriate GV if their blood glucose level is in the range of 80 mg/dL – 180 mg/dL (Group C).

The GV classification is as follows:

Group A: < 50 mg/dl.

Group B: 50 – 79 mg/dl

Group C: 80 – 180 mg/dl

Group D: 181 – 350 mg/dl

Group E: > 350 mg/dl

Safety is the last secondary outcome measure. The safety measured that will be compared in both groups include death, risk of life threatening event (i.e., severe hypoglycemia associated with seizure or altered mental status), hospitalization for diabetes complication (diabetic ketoacidosis or hypoglycemia), and risk of disability or permanent damage.

E. STATISTICAL CONSIDERATIONS

Randomization

Randomization will be performed by study statistician using random-permuted blocks of size 2 and 4. Randomization assignments will be placed in sealed, opaque envelopes to be stored. Study investigators will not be blinded to treatment assignment.

Sample Size

A goal of 20 patients is necessary for this study, but we will reach up to 40 participants in case there is any withdraw after consented and randomized. While the overall goal of the study is to demonstrate feasibility of a subsequent randomized controlled trial, limited efficacy testing will be performed. Given a sample size of 20 participants (10/grp), we will have greater than 90% power to detect a minimum standardized mean difference of 1.25 (i.e., approximately a 1.25 standard deviation difference) between groups. Effect sizes will be calculated for all study measures of interest and be used in future power calculations. On average, there are ~25 new type I/II diabetics diagnosed at Egleston hospital each month. Assuming an eligibility rate of 40%, 10 patients would be eligible to participate each month. Based on this, we are confident in our capacity to recruit 20 to 40 participants during the study period with the goal of having 20 participants to complete the study.

Statistical Analysis

Demographic characteristics will be summarized for both groups using means and standard deviations, medians and quartiles, or counts and percentages, as appropriate based on distribution. T-tests, Wilcoxon rank sums, and/or Chi squared tests will be used to assess differences between the two groups.

Primary Aims: Measures of feasibility (consent, retention, engagement, satisfaction, etc.), will be summarized overall and by group, when applicable.

Secondary Aim 1: Parental stress scale

The parental stress scale will be scored per the instrument's instructions. The total scores for the treatment groups will be compared in a cross-sectional fashion using t-tests or Wilcoxon rank sums tests as appropriate based on the distribution of scores. Changes in parental distress over-time will be evaluated using two-way repeated measures analysis of variance models. Models will include the main effect of treatment assignment, time (baseline, 1 month, 4 months), and the treatment X time interaction. The interaction term will serve as the primary statistical test for aim 2. Summary statistics, statistical significance, and effect sizes will be reported by group at each time point of interest, when applicable.

Secondary Aim 2: Glycemic variability

Glycemic variability will be examined both as a continuous variable and a categorical variable using the ranges defined in section D. Time series analysis will be used to examine daily measures of blood glucose (obtained from patient diary's) during the study period. Variability will be measured as the probability of acute change (PAC), using methods described by Jahnig et al. (2008). Acute changes will be adjusted for time between readings. In addition, first-order autocorrelations and/or mean-square successive difference will be used to examine variation in readings as described by Jahnig. Multilevel modeling will be used to test between-group differences in variability.

Secondary Aim 3: Safety

Adverse event of interest and serious adverse events (see section D) will be summarized overall and by treatment group. For participants experiencing more than 1 episode of a specific event (e.g., severe hypoglycemia), the maximum grade and severity will be recorded. Chi-square tests will be used to compare the frequency of events between the two cohorts.

Given the exploratory nature of these secondary outcomes, we will calculate effect sizes based on the adjusted means and standard deviations or differences in proportions, when appropriate.

All analyses will be conducted using SAS v9.4 (Cary, NC).

F. ANTICIPATED RESULTS

This research will be feasible to develop a successful larger clinical trial. Due to the fixed regimen seeming to be less complicated, because there are less calculations to make than in those using the ICR group, we anticipate that parental anxiety will be decreased in the FIXED group. This will encourage more blood glucose monitoring and treatment compliance. Therefore, we anticipate GV to be decreased for the FIXED group.

G. LIMITATIONS

The major limitations of this study are related to caregiver's self-completion questionnaire and ability to contact study personnel frequently during the study period in order to report blood glucose levels and implement the insulin adjustments. More than likely, multiple insulin regimens should work, but the idea behind this study is that the fixed regimen may be easier to implement.

[figure not shown]

Figure 2: Proposed protocol.

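### The number to be randomised is inconsistent (a fixed 20 per arm against 20 to 40 in all, with power based on 10 per arm), and the stated power above 90% is not delivered at 10 per arm under a conventional 5% test

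*Combined protocol and SAP*

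**What the plan says.** Four parts of section 5 of the combined protocol and SAP bear on the number of participants.

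- **5.A, Initial Visit:** "Recruitment of the 20 to 40 pediatric subjects will take place at the Children's Healthcare of Atlanta at Egleston".
- **5.B, Study Population:** "The plan is to enroll from 20 to 40 children and adolescent subjects with newly-diagnosed T1DM". The next sentence reads "Twenty will be randomized to the FIXED group and twenty will be randomized to the ICR group", with no condition or upper-limit wording.
- **5.D, Primary Outcome Measures:** the feasibility criteria include "study retention (>90% retention").
- **5.E, Sample Size:** the paragraph opens with "A goal of 20 patients is necessary for this study, but we will reach up to 40 participants in case there is any withdraw"; the losses meant are those that follow consent and randomisation. The power statement begins "Given a sample size of 20 participants (10/grp), we will have greater than 90% power" and refers to a standardised mean difference of 1.25. The paragraph ends by expressing confidence in recruiting 20 to 40, "with the goal of having 20 participants to complete the study".

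The documents give no alpha, no sidedness, no expected dropout rate, no reason for choosing 40 as the ceiling, and no rule for closing enrolment between 20 and 40. Section 12 plans periodic review of attrition but does not link it to the enrolment number.

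**The concern.** A team following section 5.B would randomise 40. A team following section 5.E could stop at 20, or anywhere up to 40. The two sizes differ by a factor of two, and the power differs with them.

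Three things depend on the answer. The first is the power statement, which is attached to the smaller size and looks too high for it. The second is retention, a primary feasibility criterion, whose denominator is not defined in a plan that enrols further participants to cover withdrawals. The third is the end of enrolment, which is left to discretion in a trial whose investigators are not blinded to assignment.

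**Working it through.** **Inputs.** Difference 1.25 SD; 10 per group (5.E) or 20 per group (5.B); retention above 90% (5.D); 20 completers wanted and a ceiling of 40 (5.E). Equal allocation is inferred from the equal arms and the blocks of 2 and 4. Alpha and sidedness are not stated, so a range is shown. The test is taken as a two-sample t-test, one of the two cross-sectional tests that 5.E names for the stress score.

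**1. The plan's own power figure.** Power comes from the noncentral t distribution with 2n − 2 degrees of freedom and noncentrality 1.25 × √(n/2). At n = 10 per group this is 1.25 × √5 = 2.80 on 18 degrees of freedom.

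| n per group | two-sided 5% | one-sided 5% | one-sided 10% |
|---|---|---|---|
| 10 | 75.3% | 85% | 92.6% |
| 20 | 97.1% | 98.7% | 99.6% |

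Two-sided 10% gives the same 85% as one-sided 5%. The normal approximation at 10 per group gives 79.8%, 87.5% and 93.5% in the three columns. So power above 90% at 10 per group is reached only at one-sided 10%. At two-sided 5%, 90% power needs 15 per group (power 91.0%; 14 per group by the normal approximation), or a difference of 1.53 SD at 10 per group.

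**2. Which numbers conflict.** Recruiting 20 to 40, aiming for 20 completers and basing power on those 20 (10 per group) can be read as one plan. An unconditional 20 + 20 = 40 randomised cannot be added to it.

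**3. Retention.** Retention = completers / randomised.

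- 20 completers from 40: 20/40 = 50%.
- 20 completers from 22: 20/22 = 90.9%, which meets the criterion. From 23: 20/23 = 87.0%, which does not. So 20 completers satisfy the criterion only if at most 22 were randomised.
- If 40 are randomised, 36/40 = 90.0% is not above 90%, so at least 37 must complete.
- Sizing for 20 completers at exactly 90% retention gives 20/0.9 = 22.2, that is 23, or 24 for equal arms. This is far below 40.
- The denominator matters. If 24 were randomised, 4 withdrew and 20 completed, retention over all randomised is 20/24 = 83.3%. With the 4 withdrawn participants left out it would be 20/20 = 100%.

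**4. End of enrolment.** Section 5.E expects 10 eligible patients a month, and the consent criterion in 5.D is above 70%, so about 7 a month if accrual is steady (an assumption). The 20th participant would enrol at 20/7 = 2.9 months and reach the 4-month visit at about 6.9 months. By then 7 × 6.86 = 48 could have enrolled. If enrolment stayed open until 20 had finished, the ceiling of 40 would be reached even with no dropout.

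**The case against.** The best defence is that only one sentence is out of line. The 20 in section 5.E is the number needed and the number to complete, 40 is a contingency ceiling, and the sentence in 5.B could be read as the allocation if the ceiling is reached. Primary feasibility measures are only summarised, efficacy testing is described as limited, and retention can be calculated for any total. Much of this stands, and it rules out several stronger readings that a reader might infer.

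- **Three rival targets (20, 20 to 40, and 40).** Not supported: the first two can be reconciled. Only the fixed 20 per arm cannot.
- **A ceiling of 40 contradicts the retention criterion.** Not supported: the criterion is a success threshold and the ceiling is an allowance. Neither forecasts 50% loss, and a pilot may budget for missing its own threshold. What remains is an allowance with no stated dropout assumption.
- **A completers-only analysis is planned, or refilling places will bias the comparison.** Not supported: no text restricts the analysis to completers, section 5.D says glycemic variability is calculated in all subjects, and differential dropout could bias a trial of fixed size as well.
- **The power statement is wrong at every size.** Not supported: 97% at 20 per arm is above 90%. The statement fails at the size it names.

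On power, one could argue that a baseline-adjusted analysis does better. Dividing 1.25 by √(1 − r²) gives about 91% at 10 per group and two-sided 5% if the baseline correlation r is 0.6, but 86% if r is 0.5. The documents give no correlation and do not tie the power statement to such an analysis, so this does not rescue it.

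The defence does not remove the unconditional 20 per arm, the missing rule for ending enrolment, or the shortfall in power at 10 per group.

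**Conclusion.** The point holds as an internal inconsistency together with a power figure that does not reproduce under a conventional 5% alpha. The total differs by a factor of two between sections 5.B and 5.E. The power shortfall at 10 per group is about 15 percentage points at two-sided 5% (75% against more than 90%) and about 5 points at one-sided 5%. It disappears only at one-sided 10%, an alpha that the documents do not state. These figures assume a two-sample t-test, equal arms and no baseline adjustment.

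The retention part is weaker: an unexplained allowance of up to 50% loss beside a criterion of more than 90%, with no stated denominator. It is a gap to fill and does not show that the criterion will be missed. For a pilot the consequence is moderate, but it touches a primary outcome and the sample-size justification.

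**What to change.** - State one randomisation target per arm, the same in Initial Visit, Study Population and Sample Size, and within the existing ceiling of 40.
- Give the dropout assumption behind that target, and a fixed point at which enrolment ends.
- Restate the power for that number with alpha, sidedness and test. At two-sided 5% with a t-test it is about 75% for 10 per arm and 97% for 20 per arm. If the sponsor wants to keep 90%, 15 analysed per arm are needed; at 90% retention that is 30/0.9 = 33.3, so 34 randomised (17 per arm).
- Define retention as completers divided by all randomised, including any withdrawn participants whose places were refilled.

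The cost is protocol wording and, if the smaller size is kept, a less favourable power figure. No participants beyond those already allowed are needed.

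### Recruitment capacity is judged only by a consent rate above 70%, which does not respond to how many families are eligible and has no defined denominator

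*Combined protocol and SAP*

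**What the plan says.** Section 5.A, Specific Aim 1, sets up the feasibility work "in order to determine the capacity for recruitment, caregiver consent to random assignment and completion of study measures", along with attendance, adherence and satisfaction. Recruitment capacity and consent to randomisation are separate items there.

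Section 5.D.1 (Primary Outcome Measures) joins them: "we will examine our ability to recruit and consent patients (>70% consent rate". No other criterion in that section concerns recruitment, and the numerator and denominator of the rate are not given.

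Section 5.E (Sample Size) gives the planning figures: "there are ~25 new type I/II diabetics diagnosed at Egleston hospital each month", and "Assuming an eligibility rate of 40%, 10 patients would be eligible to participate each month". It concludes that "we are confident in our capacity to recruit 20 to 40 participants during the study period". The length of that period is not stated. The analysis text says: "Measures of feasibility (consent, retention, engagement, satisfaction, etc.), will be summarized overall and by group, when applicable". The monitoring plan in section 12 covers consent, attrition and safety, and does not mention accrual or eligibility.

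Two further places bear on the denominator. Inclusion criterion 4 (section 5.B.1) reads "Have the ability to understand and be willing to adhere to the study protocol". The Recruitment & Consent text in section 5.A uses one hospital contact "to explore his/her interest in the study and to confirm eligibility".

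**The concern.** Feasibility is the primary goal, and the stated hypothesis is that enough patients can be recruited to support a larger trial. Whether there are enough depends on the flow of eligible patients and on the share who agree. The plan sets a success threshold only for the second.

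The first is the weaker input. The 40% eligibility rate has no cited source and is applied to type 1 and type 2 diagnoses together. Enrolment requires type 1 diabetes, age 8 to 14, English or Spanish, and none of 14 exclusions, among them a BMI above the 85th percentile. The pilot could therefore declare recruitment feasible without testing the assumption that a larger trial would most depend on.

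The second problem concerns the consent rate itself. With no denominator defined and willingness to adhere written into eligibility, a family that declines can be recorded either as a refusal or as not meeting criterion 4. The same families could then give opposite results on a primary outcome.

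**Working it through.** **Inputs from the documents.** About 25 diagnoses a month, 40% eligibility and a target of 20 to 40 (section 5.E); consent threshold above 70% (section 5.D.1).

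**Assumed inputs.** Consent of 75%, chosen because it meets the threshold (exactly 70% would not). Eligibility of 20% and 10%, as alternatives to the plan's 40%.

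**Step 1: the plan's own figure.** Eligible per month = diagnoses × eligibility = 25 × 0.40 = 10. This reproduces exactly.

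**Step 2: response of the criterion to eligibility.** Enrolled per month = 25 × eligibility × consent. Months to 20 = 20 / enrolled per month.

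| Eligibility | Eligible per month | Enrolled per month at 75% consent | Months to 20 | Consent above 70%? |
|---|---|---|---|---|
| 40% (plan) | 10 | 25 × 0.40 × 0.75 = 7.5 | 2.7 | yes |
| 20% (assumed) | 5 | 25 × 0.20 × 0.75 = 3.75 | 5.3 | yes |
| 10% (assumed) | 2.5 | 25 × 0.10 × 0.75 = 1.9 | 10.7 | yes |

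Enrolment falls by a factor of four from the first row to the last, and the result on the criterion is the same. It also does not depend on the numbers behind the ratio: 3 of 4 and 15 of 20 are both 75% and both pass, although the exact 95% intervals are 19% to 99% and 51% to 91%. This step holds whichever denominator is used.

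**Step 3: effect of the undefined denominator (illustrative counts).** Take 10 families who meet every clinical criterion, of whom 6 consent and 4 decline.

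- All decliners counted as refusals: 6/10 = 60%, criterion not met.
- Two decliners logged as failing criterion 4: 6/(10 − 2) = 6/8 = 75%, criterion met.

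In general, consent among all clinically eligible families = share classed as willing × consent among those so classed. If 70% are classed as willing (assumed) and 90% of these consent, the result is 0.70 × 0.90 = 63%, against a recorded 90%. This step applies only if the denominator is families meeting all inclusion criteria. If it is everyone approached, decliners stay in and the rate remains 60%.

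**The case against.** The plan does state a target of 20 to 40 participants with 20 completers, so a shortfall would be seen. The list of feasibility measures is open-ended, so recruitment counts are not ruled out. This stands in part: recruitment would not go unobserved. But the target is not among the success criteria in section 5.D.1, and with no time frame even slow accrual eventually reaches 20.

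On the denominator, criterion 4 speaks of subjects rather than caregivers and does not mention randomisation. A parent who refuses randomisation is most naturally a consent refusal. Potential eligibility is also assessed under a HIPAA waiver before contact, when willingness cannot be known. All of this stands. A reader might infer that the consent rate is biased upward. The documents do not support that: they leave the denominator open, and inflation follows from one permitted reading. A reader might also cite daily glucose reporting as a trial burden that drives refusals, but section 5.A presents it as standard care.

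The lower eligibility rates are assumptions. Because the study period has no stated length, 10.7 months is not shown to be a failure. That is correct; the table shows that the criterion is insensitive, not that recruitment will be slow.

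Finally, one could multiply the plan's 10 a month by 70% and treat 7 enrolments a month as the required rate. The plan states no such figure. As a mandatory gate it would call recruitment infeasible at 6 a month, although 20 would then be reached in 20/6 = 3.3 months.

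**Conclusion.** The point holds. The aim asks two questions and the success criterion answers one. With consent fixed at 75%, the criterion is met equally at 7.5, 3.75 and 1.9 enrolments a month. That conclusion needs no assumption about the denominator; the 75% and the two lower eligibility rates only illustrate it. The consequence is that the >70% criterion cannot test the 40% eligibility assumption or the hypothesis of enough patients.

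The denominator problem is a narrower one. The rate can be inflated (60% to 75% in the example) if some decliners are classed as ineligible under criterion 4. Whether this would happen, and how often, cannot be determined from the documents. The change should be made before enrolment, because screening decisions that are not tallied as they occur may be hard to reconstruct.

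**What to change.** In section 5.D.1, replace the single criterion with two, and carry both into the feasibility analysis in section 5.E.

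(a) **Consent rate:** consented / all approached families who meet inclusion criteria 1, 2, 3 and 5 and no exclusion. Anyone unwilling to adhere or to be randomised counts as a refusal. The 70% threshold can stay.

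(b) **Recruitment capacity:** eligible patients (same definition) / all new-onset diabetes admissions screened, and eligible patients per month, compared with the plan's own 40% and 10 a month. Add participants randomised per month and the time to reach 20, against a time frame that the sponsor states. Do not impose 7 a month as a gate.

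Report the counts screened, eligible, approached, consented and randomised. Conclude that recruitment is feasible on (a) and (b) together, not on the consent rate alone.

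The tally must cover all new-onset diabetes admissions. The 40% refers to type 1 and type 2 diagnoses combined, whereas the waiver screening is described for type 1 only. Section 5.B already draws subjects from all such admissions, so the population is accessible, but the tally may be some extra work. The other costs are protocol wording, a consent rate that may look lower, and a second recruitment measure that may be missed. Visits, procedures and sample size do not change.
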